1.3.9 Data management

The CUMC Division of Family Planning and Preventive Services currently employs a research manager and five research coordinators who will be available to assist with this study. The research manager will assist the investigators with IRB preparation and submission, staff training manuals, and will carry out data monitoring. We will assign some study tasks to research coordinators depending on expertise and availability. If necessary, we will hire a new research coordinator to assist with data management.

We will collect all study data using paper forms. The central research office staff will obtain logs, distribute study forms to sites, and collect data for every 10-20 enrollments at each site, or at least on a twice monthly basis. Study coordinators will be responsible for abstracting data from all patient charts and using study forms to compile this information, as described in section 1.3.1.c. Investigators will review 10% of charts abstracted by study coordinators in order to assess adherence to standardized data collection and recording. Investigators will develop a study database in Research Electronic Data Capture (REDCap), a mature, secure, web-based application for building and managing surveys and databases. This system has been IRB-approved for use here at CUMC and research office staff is familiar with its use. Using single data entry, research staff will enter all data from research forms into this database. Following data entry, all forms will be stored in a locked file cabinet in the research office until study completion and manuscript publication.

All staff members involved with data management will be required to complete CUMC's Research Compliance and Administration System (RASCAL) and HIPAA trainings. Only research team members will be permitted access to study data. All data will be managed on CUMC-encrypted computing devices which are password-protected, fire-walled devices linked to a secure server located within the Department of Obstetrics and Gynecology.

1.3.10 Data analysis

First, we will evaluate baseline characteristics of all women entered into this study. We will also evaluate if randomization was successful in creating comparable groups. We will use a test of difference in proportions to compare outcomes in this study. We will compare the overall proportions with additional testing. We will also compare acceptability of TVS vs. TAS and assess satisfaction. For our secondary analyses, we will compare subgroups defined by provider and provider type, clinic site, and based on clinical characteristics including GA, BMI, and previous C/S. We will evaluate whether there is a difference in the proportion receiving additional tests in the TVS and TAS groups that is associated with any of these variables (physician provider compared to APC provider, Ob/Gyn physician compared to Family Medicine physician, obese participant compared to normal weight participant, etc.). We will use SAS to analyze our findings, as both fellows currently have access to SAS and use it routinely as part of graduate school studies.

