1.1.2 Objectives and hypotheses

We hypothesize that for the majority of patients seeking medical abortion, history plus TAS will be comparable (non-inferior) to history plus TVS in the assessment of medical abortion eligibility. In our own recent clinical experience, approximately 5.1% (standard error 2.0%) of patients required further clinical testing after TVS before determination of eligibility. Conversely, 94.9% of patients did not require additional testing. Our objectives include:

Primary Outcomes:

1. **Hypothesis 1:** We hypothesize that history and TAS will be sufficient to determine eligibility in more than 80% of patients (thus our non-inferiority boundary is 80%).
 - a. Evaluate how often the provider orders additional tests (see table 1, in Appendix) prior to providing medical abortion, but after:
 - i. History plus TAS or,
 - ii. History plus TVS
 - b. Evaluate whether the results for TAS exceed the non-inferiority boundary of 80%

2. Hypothesis 2: We hypothesize that patient satisfaction and acceptability will be greater for TAS compared to TVS, based on visual analog scale rating performed by patients following visit. We found no direct data to inform us about the likely size of the difference in acceptability of TVS compared to TAS, as this has not previously been studied (see Section 1.2).
 - a. Assess which ultrasound modality is preferable (“In the future, if you had the choice to receive either TVS or TAS, which would you prefer?”)
 - b. Evaluate if acceptability varies according to patient characteristics including:
 - i. Gestational age
 - ii. Ultrasound experience
 - iii. Abortion or other obstetric experience
 - iv. Additional factors (e.g. age)

Secondary Outcomes: Identify patient and provider characteristics associated with ordering additional tests:

- a. Gestational age (GA) by LMP (≤ 35 days vs. 35-49 days vs. > 49 days, vs. uncertain GA)
- b. Body mass index (BMI) and history of Cesarean delivery
- c. Provider type or experience (physician, APC)
- d. Site (CUMC, PPCGNNJ)
- e. Secular trends within the study (first third of patients seen by providers vs. last third of patients)
- f. Early pregnancy failure

Note: The use of sonography or other strategies for follow-up and cost-effectiveness analyses are also important, but are beyond the scope of this project.

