Our base assumption is that 5-7.5% of patients will need additional testing after TVS. We also expect to see the greatest variability between TVS and TAS findings between 35 and 49 days estimated gestational age, compared to those less than 35 days and greater than 49 days. Prior to 35 days, we expect neither TVS nor TAS to be able to identify a gestational sac for most women (thus resulting in additional testing in both groups), and after 49 days we expect both TVS and TAS to usually be able to identify a gestational sac with fetal pole (thus resulting in less additional testing in both groups). Between 35 and 49 days, however, we expect some proportion of patients to have a gestational sac with or without a yolk sac identifiable on TVS but not on TAS and in this range, the proportion of patients for whom clinicians order additional tests may be higher. We expect the proportion where providers encounter uncertainty, leading to additional testing, would be greater at earlier gestational ages and perhaps in those patients with an uncertain LMP or irregular cycle (questions we will be formally evaluating as described in Hypothesis #1, section 1.1.2).

Further, we expect clinicians to order more testing after TAS because TAS has lower resolution than TVS. The transabdominal probe is further from the uterus, and thus uses a lower frequency to achieve a longer focal length. TAS typically uses a 3-6 mHz probe while TVS uses a probe with 5-10 mHz frequency. TAS may have even less resolution in an obese patient as the distance to the uterus will be greater; obesity's effect of decreasing resolution was noted in a prior study by Lohr et al.⁶³

We expect additional testing after TVS to mainly include serial quantitative beta-hCG tests and additional visits for a repeat sonogram. We expect that additional testing after TAS would include the same, plus same-day use of TVS if TAS inadequate to confirm eligibility for medical abortion. At all study sites, immediate TVS will be available

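### Sections 1.1.2 and 1.3.10 pose two different secondary questions, and the one test given does not address whether the TAS-minus-TVS difference varies between subgroups

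*Combined protocol and SAP*

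**What the plan says.** Section 1.1.2 gives the secondary outcome as: "Identify patient and provider characteristics associated with ordering additional tests". It lists gestational age, BMI and Cesarean history, provider type or experience, site, secular trend and early pregnancy failure. No contrast between arms appears in that wording.

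Section 1.3.10 gives the analysis. It opens with one method: "We will use a test of difference in proportions to compare outcomes in this study". It then says: "For our secondary analyses, we will compare subgroups defined by provider and provider type, clinic site, and based on clinical characteristics". The aim is stated as finding whether there is a "difference in the proportion receiving additional tests in the TVS and TAS groups that is associated with any of these variables", and the contrasts given as examples are "physician provider compared to APC provider, Ob/Gyn physician compared to Family Medicine physician, obese participant compared to normal weight participant".

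The protocol contains no interaction term, regression model, test of homogeneity, effect scale or subgroup-specific risk difference.

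Section 1.3.11 sets out what is expected for gestational age: "We also expect to see the greatest variability between TVS and TAS findings between 35 and 49 days estimated gestational age". It also says: "Prior to 35 days, we expect neither TVS nor TAS to be able to identify a gestational sac for most women", so that more testing follows in both arms, and it expects less testing in both arms after 49 days.

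**The concern.** Section 1.1.2 asks whether a characteristic predicts additional testing. Section 1.3.10 asks whether it changes the gap between TAS and TVS. A variable can do either without the other, so one comparison cannot serve both. The listed contrasts set one subgroup against another, which is the form of the first question.

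Gestational age shows the difficulty in the protocol's own terms. Below 35 days, both arms are expected to have more testing; above 49 days, both are expected to have less. A comparison of those two groups should therefore find a difference whether or not the TAS penalty differs between them.

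What is at stake is the practical message. Section 1.1.1 says the results could guide settings without TVS on which patients they could serve. That guidance needs the TAS-minus-TVS difference within each type of patient. If a general predictor of testing is reported as a factor that worsens TAS, or a real difference in the TAS effect is overlooked, the guidance is wrong for those patients.

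**Working it through.** **Inputs from the documents.** Allocation is 1:1 (section 1.3.3). Table 3, row 1, gives 5% after TVS, 10% after TAS, a 10-point margin and 340 per arm. That size reproduces: (1.645 + 0.842)² × (0.95×0.05 + 0.90×0.10) / (0.10 − 0.05)² = 340.04. So N = 2 × 340 = 680. The summary's planned enrolment of about 800 is the other value used. The documents give no figure for the subgroup analyses.

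**Assumptions.** Subgroup rates are illustrative. The level is taken as two-sided 5%, because section 1.3.10 states none for secondary analyses. The first-listed subgroup makes up 20%, 30% or 50% of the women.

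**What each contrast estimates.** For subgroups A and B, let d(TVS) and d(TAS) be the A-minus-B difference in testing within each arm.

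- Subgroup comparison, arms pooled: [d(TVS) + d(TAS)] / 2
- Effect modification on the risk-difference scale: d(TAS) − d(TVS)

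One is an average and the other a difference. Neither fixes the other.

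**Constant TAS effect, prognostic factor.** Take TVS 10% vs 3% and TAS 15% vs 8%. Then d(TVS) = d(TAS) = 7 points, so effect modification is 7 − 7 = 0 while the pooled contrast is 7 points (12.5% vs 5.5%). At N=680 split evenly, the standard error is √[(0.125×0.875 + 0.055×0.945)/340] = 0.0218. So z = 0.07/0.0218 = 3.21, and rejection is about Φ(3.21 − 1.96) = 89%.

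With TVS 6% vs 4% and the same 5-point effect, the pooled rates are 8.5% vs 6.5%. Then z = 0.02/0.0202 = 0.99, and rejection is about Φ(0.99 − 1.96) = 17%.

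Simulated rejection over N=680 to 800 and the three subgroup shares:

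| Assumed TVS rates (TAS adds 5 points in both) | Subgroup test, arms pooled | Interaction test |
|---|---|---|
| 10% vs 3% | 77-94% | about 5% |
| 6% vs 4% | 14-19% | about 5% |
| 5% vs 5% (not prognostic) | about 5% | about 5% |

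**Other readings of the method.** The text does not say the arms are pooled, so two alternatives were checked.

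- Subgroups compared within each arm: with TVS 2.5% vs 7.5% and TAS 7.5% vs 12.5% (5 points in both), at least one arm is significant in 71-78% of trials (subgroup shares of 30-50%).
- TAS against TVS tested separately in each subgroup: with TVS 10% vs 3% and equal 5-point effects, one subgroup is significant and the other is not in 51-71% of trials.

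Neither has equal TAS effects as its null hypothesis.

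**Real effect modification.** With TVS 10% vs 3% and TAS 10% vs 17%, TAS adds 0 points in one subgroup and 14 in the other. The arm-averaged rates are 10% in both. The pooled subgroup test rejects in about 5% of trials and the interaction test in 69-92%. When the averages do not cancel the contrast disappears: with TVS 5% vs 5% and TAS 17% vs 7%, the pooled test has 52-73% power and the interaction test 43-74%.

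**What an interaction test can deliver.** For 80% power with even subgroups, n per cell = (1.96 + 0.842)² × Σp(1−p) / δ².

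- For δ = 10 points (rates 7.5%, 7.5%, 2.5%, 12.5%): 7.849 × 0.2725 / 0.01 = 213.9, so 4 × 214 = 856 women.
- For δ = 5 points (rates 5%, 7.5%, 5%, 12.5%): 7.849 × 0.27375 / 0.0025 = 859.5, so 4 × 860 = 3,440 women.

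**The case against.** The strongest reply is that section 1.3.10 leaves the method open rather than choosing a wrong one. The test of proportions is introduced for the study outcomes generally. The secondary sentences say only that subgroups will be compared, and nothing says arms will be pooled or excludes an interaction analysis. This stands in part: a reader might infer that the plan commits to a pooled main-effect test, and the text does not say so. But each way of applying the stated method leaves equal TAS effects untested.

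A reader might also infer that the secondary analysis is simply mis-specified. It is not. Section 1.1.2 poses a main-effect question, and a comparison of subgroups answers it.

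Nor do the documents support saying that the method generally flags effect modification where none exists. The false signal needs a prognostic factor. Section 1.3.11 expects the TVS-TAS gap itself to vary with gestational age and suggests that TAS resolution may be worse in obese patients, so a constant effect is not what the protocol expects across those factors. The constant-effect case fits best the contrast of below 35 with above 49 days. Missing a real difference likewise depends on arm-averaged rates that happen to be similar.

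The result also depends on scale. A 5-point effect on TVS rates of 10% and 3% is a constant risk difference but gives risk ratios of 1.5 and 2.7.

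Finally, section 1.3.1.f concedes that sample size limits these analyses, and section 1.3.12 sets no power for the provider-type comparisons. That limits the consequences. It does not cure a test of a different null hypothesis, since a larger sample makes the false signal more frequent.

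**Conclusion.** The point holds in this form: the protocol states two secondary questions, and its one method can answer the section 1.1.2 question but not the section 1.3.10 question. For a factor that predicts testing in both arms, a subgroup comparison can look like a varying TAS effect when the risk difference is constant. The size ranges from about 14-19% rejection for a modest prognostic gap to 77-94% for a large one, against about 5% for an interaction test, and there is no excess if the factor is not prognostic. These figures rest on assumed subgroup rates, pooled arms and a two-sided 5% level. The failure to detect real effect modification is possible but is the weaker half of the argument.

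The change is worth making because a better method is available at almost no cost. A reader might infer that the trial's main conclusion is at risk; it is not. The primary comparison does not use these analyses, which are secondary and acknowledged as limited.

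**What to change.** In section 1.3.10, say which analysis answers which question.

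- **Does the TAS-minus-TVS difference vary (section 1.3.10)?** Prespecify an arm-by-factor interaction on the risk-difference scale, which is the scale of the non-inferiority margin. For example, fit a binomial model with arm, factor and their product. Report the TAS-minus-TVS risk difference with a 95% CI in each level of each factor. Label the results exploratory and claim no multiplicity control.
- **Which characteristics go with ordering tests (section 1.1.2)?** Keep the subgroup comparisons, adjusted for arm, and state that they will not be interpreted as differences in the TAS effect.

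The cost is a few sentences and a few lines of SAS, with no new data. The drawback is limited power: about 856 women are needed for a 10-point interaction and 3,440 for a 5-point one, under the rates assumed above. Many interaction results will therefore be inconclusive, in line with the limitation already stated in section 1.3.1.f, and the intervals will be more informative than the p-values.

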1.3.11 Number of subjects and statistical power

This randomized study among women seeking medical abortion will compare the proportion of women who require additional testing after either TVS (usual care) or TAS (the intervention). The study also will

compare patient satisfaction with TVS compared to TAS. The first objective (comparing rate of additional testing) drives the sample size calculations. Table 3 provides the results; below we present our analysis.

Our estimate of additional testing ordered after TVS comes from our own clinic where a new fellow without previous medical abortion experience ordered additional tests (see table 1) in 9 out of 120 patients (7.5%, standard error $\pm 2.4\%$). On further analysis, 3 of these patients had previously been seen for possible miscarriage or pregnancy of unknown location. Therefore, 6 of 117 patients referred specifically for medical abortion received additional testing (5.1%, standard error $\pm 2.0\%$). The main reason for ordering additional tests was the inability to identify an intrauterine pregnancy by TVS. Most of these patients received a combination of serial quantitative hCG levels or repeat sonography; all were ultimately found to have very early intrauterine pregnancies identified upon follow-up. The rate of additional testing ordered might be lower in the hands of more experienced clinicians and sonographers; however, we are unaware of any other estimates. Performing additional chart abstraction in preparation for the study (described above) will permit a more precise estimate of further testing at these sites.

Our base assumption is that 5-7.5% of patients will need additional testing after TVS. We also expect to see the greatest variability between TVS and TAS findings between 35 and 49 days estimated gestational age, compared to those less than 35 days and greater than 49 days. Prior to 35 days, we expect neither TVS nor TAS to be able to identify a gestational sac for most women (thus resulting in additional testing in both groups), and after 49 days we expect both TVS and TAS to usually be able to identify a gestational sac with fetal pole (thus resulting in less additional testing in both groups). Between 35 and 49 days, however, we expect some proportion of patients to have a gestational sac with or without a yolk sac identifiable on TVS but not on TAS and in this range, the proportion of patients for whom clinicians order additional tests may be higher. We expect the proportion where providers encounter uncertainty, leading to additional testing, would be greater at earlier gestational ages and perhaps in those patients with an uncertain LMP or irregular cycle (questions we will be formally evaluating as described in Hypothesis #1, section 1.1.2).

Further, we expect clinicians to order more testing after TAS because TAS has lower resolution than TVS. The transabdominal probe is further from the uterus, and thus uses a lower frequency to achieve a longer focal length. TAS typically uses a 3-6 mHz probe while TVS uses a probe with 5-10 mHz frequency. TAS may have even less resolution in an obese patient as the distance to the uterus will be greater; obesity's effect of decreasing resolution was noted in a prior study by Lohr et al.⁶³

We expect additional testing after TVS to mainly include serial quantitative beta-hCG tests and additional visits for a repeat sonogram. We expect that additional testing after TAS would include the same, plus same-day use of TVS if TAS inadequate to confirm eligibility for medical abortion. At all study sites, immediate TVS will be available

1.3.12 Study limitations

Our project is a randomized controlled trial that will aid us in better answering the question of whether TAS provides sufficient information or changes the need for further testing to determine medical abortion eligibility, when compared to TVS. Providers' judgment still may have an important effect on our clinical outcomes, however, our endpoint is whether the provider orders a test or not.. Subjectivity is certainly possible, even likely, but our design replicates the real-world healthcare setting in which providers currently routinely use TVS. We are using the PractiHC extension to the CONSORT guidelines to assist us in designing this study in a way that will provide useful information for our health-services study question.

We anticipate possible differences in outcomes based on provider type and experience. For this reason, we are attempting to include a variety of providers and analyze these differences, as discussed above. We may have difficulty enrolling a sufficient number of patients for certain provider types (such as family physicians) to demonstrate any real differences in proportions between groups and are therefore not basing our power calculations on such planned analyses. We visited multiple family medicine clinics in preparation for this study, but ultimately excluded these study sites due to low medical abortion volume. Additional details regarding practice volume at proposed study sites within CUMC and PPCGNNJ are included in Table 1.

1.3.13 Duration of project

The anticipated duration of this project will include eight months for enrollment and an additional six months for data analysis.

1.4 Project management

The primary faculty mentor for this study is [name], with additional mentorship by [name]. Planned Parenthood of Central and Greater Northern New Jersey is the only site outside of CUMC where we will be enrolling providers and patients. [name] will be primarily responsible for analyzing data regarding the proportion of women who receive additional testing and [name] will be focusing on analysis of the patient satisfaction data. Both fellows will share responsibility for preparation of study documents and protocols, and for training providers and coordinators on study protocols. Both fellows will also analyze data regarding secondary outcomes, following work on primary outcomes.

1.5 Links with other projects

Gynuity Health Projects is currently running a single-arm trial with approximately 300 participants evaluating “no-touch” medical abortion. While not directly linked, our study’s findings will complement their research and contribute to the body of literature on methods of determining medical abortion eligibility that could help improve access and decrease costs.

1.6 Main problems anticipated

We anticipate some challenges integrating study protocols with preexisting workflows at the research sites. Some locations use ancillary staff for portions of the patient evaluation, such as medical assistants collecting basic history information, or other staff members performing sonography. To assess any disruption in workflow and associated redundancies or delays, we interviewed multiple medical abortion providers, including those working at our proposed study sites, to clearly identify the range of clinic workflows, and consider approaches to integrating study protocols that would be less disruptive. We anticipate that the main potential disruption to workflow would be utilizing TAS instead of a routine TVS in these sites where it is not currently performed routinely, and have planned provider training and a run-in period to mitigate this issue (see Section 1.3.1.d.).

We are planning this project as a multicenter study, which we expect to introduce some additional challenges. While initially envisioned as a larger study at multiple sites outside of our own institution, in order to minimize challenges with IRB approval, we will enroll only providers at CUMC and PPCGNNJ and we will therefore only require CUMC and PPCGNNJ IRB approval. In addition, PPCGNNJ sites are easily accessible by public transportation and car.

This Planned Parenthood affiliate also has research experience including current participation in a large multicenter trial investigating self-administration of Depo Provera, being carried out by the Planned Parenthood Federation of America (PPFA) Research department. [name] is a co-investigator of that trial. This affiliate has excellent compliance with study protocols and has a skilled staff prepared to handle a randomized trial such as the one proposed in this study. PPFA’s study monitors have found these sites to have excellent adherence to research requirements.

